5.3 Considerations for interim analysis

For the interim analysis, the efficacy analysis in the OLE period will only focus on the primary and key secondary efficacy endpoints:

- 28-item PSPRS total score and 15-item PSPRS total score,
- MDS-UPDRS Part II, CGI-C, PSP cognitive composite battery, and PSP-QoL.

For the primary endpoint PSPRS, the following analyses will also be conducted:

- By-visit shift from baseline analysis and the by-visit categorical summary for each individual item in the 28-item PSPRS will be presented. The same analyses will be performed for each item of the 15-item PSPRS.
- The change from baseline in each of the 6 subscales of 28-item PSPRS will be summarized by visit, analyzed by MMRM and plotted over time. The same analysis will be applied to the 3 subscales of 15-item PSPRS (gait/limb, ocular motor, and bulbar).

Because too few patients will have reached Week 100 at the time of interim analysis database lock, the CSF PD analysis and the efficacy MRI analysis will not be conducted.

5.4 By Visit Summary and Mixed Model Repeated Measures (MMRM) Model

Change from baseline analyses will be performed using summary statistics and MMRM. Visits with too few data may be excluded from the MMRM analysis. Line plots for adjusted mean change from baseline over time will be provided.

Considerations for base MMRM model for change from baseline analyses

The baseline and change from baseline for a parameter of interest will be summarized by OLE treatment group at each post-baseline visit. A MMRM model will be used as the primary analysis to analyze change from baseline using fixed effects of OLE treatment group, time (categorical), OLE treatment group-by-time interaction, baseline for the parameter of interest, (baseline for the parameter of interest) by time interaction, baseline Color Trails 2 test (≤ 170 or > 170 seconds) and region. An unstructured covariance matrix will be used to model the within-patient variance-covariance errors. If the unstructured covariance structure matrix results in a lack of convergence, the heterogeneous Toeplitz covariance structure followed by the heterogeneous first-order autoregressive covariance structure will be used. The Kenward-Roger approximation will be used to estimate the denominator degrees of freedom.

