17. STATISTICAL CONSIDERATIONS

17.1. Sample Size Determination

Approximately 459 participants will be randomly assigned in a 2:1 ratio to receive BIIB092 or placebo (306 participants in the BIIB092 treatment group and 153 in the placebo group). Anticipating a dropout rate of approximately 25% (based on previous clinical studies in participants with PSP), approximately 345 participants (230 participants in the BIIB092 treatment group and 115 participants in the placebo group) are expected to complete the study through Week 52.

Using a two-sided, two-sample t-test with an alpha level set at 0.05, this sample size will provide 80% power to detect a difference of 3.2 points in the change in PSPRS total score from baseline to Week 52 for BIIB092 relative to placebo, assuming a common standard deviation of 9.95 [Stamelou 2016] in the change in PSPRS total score from baseline to Week 52.

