5.2 Visit windows for mapping efficacy endpoint

For efficacy data that are summarized or analyzed by visit, data collected on all scheduled visits and all unscheduled visits will be mapped to an appropriate analysis visit using the windowing scheme shown in Table 1. If there are 2 or more assessments available in the same analysis window for a subject, the assessment that is closest to the target visit day will be used for analysis. If there are 2 or more assessments in the same analysis window with the same distance from the target visit day, the later assessment will be used.

Table 1 Visit Windows for Primary Endpoint: PSPRS

| Analysis visit | Target visit day | Analysis visit window |
|-----------------------|-------------------------|--|
| Baseline | 1 | Most recent non-missing value on or prior to the first dose date |
| Week 12 | 85 | [43, 126] |
| Week 24 | 169 | [127, 210] |
| Week 36 | 253 | [211, 294] |
| Week 48 | 337 | [295, 350] |
| Week 52 | 365 | [351, 378] |
| Week 64 | 449 | [407, 490] |
| Week 76 | 533 | [491, 574] |
| Week 88 | 617 | [575, 658] |
| Week 100 | 701 | [659, 742] |
| Week 112 | 785 | [743, 826] |
| Week 124 | 869 | [827, 910] |
| Week 136 | 953 | [911, 994] |
| Week 148 | 1037 | [995, 1078] |
| Week 160 | 1121 | [1079, 1162] |
| Week 172 | 1205 | [1163, 1246] |
| Week 184 | 1289 | [1247, 1330] |
| Week 196 | 1373 | >=1331 |

Table 2 (a) Visit Windows for Key Secondary Efficacy Endpoints (MDS-UPDRS, CGI, PSP cognitive composite battery and PSP-QoL) and RBANS

| Analysis visit | Target visit day | Analysis visit window |
|-----------------------|-------------------------|--|
| Baseline | 1 | Most recent non-missing value on or prior to the first dose date |
| Week 12 | 85 | [43, 126] |
| Week 24 | 169 | [127,210] |
| Week 36 | 253 | [211, 308] |
| Week 52 | 365 | [309, 378] |
| Week 64 | 449 | [407, 490] |
| Week 76 | 533 | [491, 616] |
| Week 100 | 701 | [617, 784] |
| Week 124 | 869 | [785, 952] |
| Week 148 | 1037 | [953, 1120] |
| Week 172 | 1205 | [1121, 1288] |
| Week 196 | 1373 | >=1289 |

Table 3 (b) Visit Windows for Key Secondary Efficacy Endpoint PSP cognitive composite battery (13 individual subtests)

| Analysis visit | Target visit day | Analysis visit window |
|-----------------------|-------------------------|--|
| Baseline | 1 | Most recent non-missing value on or prior to the first dose date |
| Week 12 | 85 | [43, 126] |
| Week 24 | 169 | [127,210] |
| Week 36 | 253 | [211, 308] |

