5.1.4 Considerations for base MMRM model for change from baseline analyses

The observed value and change from baseline for a parameter of interest will be summarized by treatment group at each post-baseline visit. A mixed model repeated measures (MMRM) model will be used as the primary analysis to analyze change from baseline using fixed effects of treatment group, time (categorical), treatment group-by-time interaction, baseline for the parameter of interest, (baseline for the parameter of interest) by time interaction, baseline Color Trails 2 test (≤ 170 or > 170 seconds) and region (see healthcare region definitions in Section 3.1). An unstructured covariance matrix will be used to model the within-subject variance-covariance errors. If the unstructured covariance structure matrix results in a lack of convergence, the heterogeneous Toeplitz covariance structure followed by the heterogeneous first-order autoregressive covariance structure will be used. The Kenward-Roger approximation will be used to estimate the denominator degrees of freedom. If the unstructured variance-covariance structure does not converge in the MMRM model and a structured model is used, the sandwich estimator will be used to get the variance of the treatment effect estimator. The adjusted mean of each treatment group, as well as the treatment group differences will be displayed with 95% CI and p-value. In the primary analysis of each endpoint, missing data are assumed to be missing at random [Rubin 1976].

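### The OLE SAP omits the sandwich variance that the placebo-controlled SAP attaches to the same structured-covariance fallback, so early- versus late-start standard errors may be invalid if that fallback is used and does not fit

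*SAP*

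**What the plan says.** OLE SAP 5.4 analyses change from baseline with an MMRM and an unstructured covariance. If that does not converge, "the heterogeneous Toeplitz covariance structure followed by the heterogeneous first-order autoregressive covariance structure will be used". Denominator degrees of freedom come from Kenward-Roger. No variance estimator is named. The section also allows visits with too few data to be left out of the model.

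Placebo-controlled SAP 5.1.4 gives the same model form, fallback order and Kenward-Roger rule. It then adds that if the unstructured matrix fails and "a structured model is used, the sandwich estimator will be used to get the variance of the treatment effect estimator".

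Nothing in the OLE SAP brings that sentence in. Its efficacy cross-reference to the placebo-controlled SAP for method, at the end of section 5.2, concerns missing scale items only.

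The affected result is the by-visit comparison of early with late start on the pooled placebo-controlled and OLE data (OLE SAP 5.1), tested two-sided at 0.05 (3.1) with no multiplicity adjustment (5.1).

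**The concern.** Model-based standard errors from an MMRM with missing data are correct only if the assumed covariance is correct. Heterogeneous Toeplitz and heterogeneous AR(1) both give every adjacent pair of visits the same correlation. In OLE SAP Table 1, Week 48 has target day 337 and the next row is "Week 52 | 365 | [351, 378]", so that gap is 28 days; the other PSPRS gaps are 84 days. In a progressive disease where patients decline at different rates, a structure that ignores spacing is unlikely to be exact. The sponsor's own placebo-controlled plan provides a robust variance for this situation.

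The fallback is also more likely to be needed in the OLE model, which has more visits and thinner late data. At stake are the confidence intervals and p-values of the extension's by-visit efficacy comparison, most of all around Weeks 52 to 76, when late-start subjects have just switched to active treatment.

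**Working it through.** **1. The plan's own figure.** Protocol 17.1 gives "Using a two-sided, two-sample t-test with an alpha level set at 0.05", "assuming a common standard deviation of 9.95" and 230 versus 115 completers.
- SE = 9.95 × √(1/230 + 1/115) = 1.136.
- 3.2/1.136 = 2.816, and Φ(2.816 − 1.960) = 80.4% (80.2% with the t distribution).

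This agrees with "this sample size will provide 80% power to detect a difference of 3.2 points". It does not depend on the point at issue; it fixes the SD scale used below.

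**2. Covariance parameters for PSPRS.** With k visits, unstructured needs k(k+1)/2, heterogeneous Toeplitz 2k−1 and heterogeneous AR(1) k+1.

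| Model | Visits | Unstructured | Toeplitz | AR(1) |
|---|---|---|---|---|
| Placebo-controlled | 5 | 15 | 9 | 6 |
| OLE, Weeks 12 to 88 | 8 | 36 | 15 | 9 |

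**3. Size of the error if the fallback is used.** Inputs from the documents: PSPRS visits at Weeks 12, 24, 36, 48, 52, 64, 76 and 88; 306 versus 153 subjects; SD 9.95 at Week 52; 25% dropout by Week 52.

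Assumptions not in the documents:
- fractions observed of 95, 89, 83, 77, 75, 60, 40 and 20% at those visits;
- monotone dropout, completely at random and equal in both arms;
- the true covariances below, with y = weeks/52, each scaled to variance 9.95² = 99.0 at Week 52.

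Method: for each true covariance V, find the Toeplitz or AR(1) matrix S that fits best over the dropout patterns (smallest average Gaussian divergence). Let p_k be the share of subjects last seen at visit k.
- Model-based variance: A⁻¹, where A = Σ p_k S_k⁻¹.
- True variance: A⁻¹BA⁻¹, where B = Σ p_k S_k⁻¹V_kS_k⁻¹.
- Multiply each by (1/306 + 1/153). With r = model-based SE / true SE, the error of a nominal 5% test is 2[1 − Φ(1.96 r)].

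Example (moderate slopes, Toeplitz, Week 64): r = 1.143/1.291 = 0.885; 1.96 × 0.885 = 1.735; error 8.3%.

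| True covariance | r, Weeks 52–76 | Error, Weeks 52–76 | r, Week 12 |
|---|---|---|---|
| Moderate random slopes: 70yy′ + 14.5J + 14.5I | 0.88–0.92 | 7.3–8.4% | 1.19–1.20 |
| Strong random slopes: 90yy′ + 4.5J + 4.5I | 0.81–0.86 | 9.2–11.2% | 1.32–1.40 |
| Correlation exp(−weeks apart/60), SD 9.95√y | 0.95–1.01 | 4.9–6.4% | 1.02 |
| Constant correlation: 50J + 49I, Toeplitz | 1.00 | 5.0% | 1.00 |
| The same, AR(1) | 1.01 | 4.7–4.9% | 1.00 |

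(J is the matrix of ones, I the identity.) A heterogeneous AR(1) truth gives exactly 5.0% with either fallback. A separate calculation with five random-slope covariances, nine visits to Week 100 and thinner follow-up (49% observed at Week 64, 32% at Week 76, 4% at Week 100) gave 5.8 to 9.1% at Weeks 52 to 76.

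**4. Does the sandwich repair it?** A simulation with 306 versus 153 subjects, that thinner follow-up, random-slope truths and the working covariance held at its best fit gave:
- Weeks 52 to 76: 4.3–6.1% with the sandwich, 6.2–9.8% model-based.
- Week 100, where 4% of 153 is about 6 late-start subjects: 8.2–8.7% with an uncorrected sandwich, 1.4–2.0% model-based. Under constant correlation: 10.2% against 4.4%.

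**The case against.** **It is doubly conditional.** The unstructured model must fail and the fallback must misfit. A reader might infer that the standard errors would be wrong whenever the unstructured model does not converge, or that both structures are wrong by construction. The documents do not support either reading: constant correlation with unequal variances is a special case of heterogeneous Toeplitz whatever the spacing, and the table shows essentially no effect there. This stands, and the point is worded accordingly.

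**Sparse visits can be dropped.** Table 1 lists 17 post-baseline PSPRS visits, which would mean 17 × 18/2 = 153 unstructured parameters. That is tempting but unrealistic here. OLE SAP 3.1 limits this SAP to an interim analysis, 5.3 expects too few patients at Week 100, and 5.4 allows sparse visits to be excluded. This stands for the likelihood of fallback. But exclusion is optional, the criterion is undefined, and it does not correct the variance once fallback occurs.

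**The stakes are limited.** Long-term efficacy is a tertiary OLE endpoint, tested visit by visit without multiplicity control. A reader might fear for the primary analysis, but the Week 52 primary test is governed by placebo-controlled SAP 5.1.4, which has the sandwich. The protocol's own fallback for the primary MMRM (17.4.1) names no sandwich either, so the OLE SAP does not depart from the protocol. All of this stands.

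**Intent and estimator are inferred.** The documents do not show that the sentence was deliberately removed, and 5.4 never says model-based. That is simply the natural reading of Kenward-Roger with no robust estimator named.

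**The remedy has limits.** An uncorrected sandwich can be anti-conservative at very sparse visits, as step 4 shows. Nor does it remove bias in the estimate when a misspecified covariance meets data missing at random but not completely at random. The first limit shapes the fix.

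**Conclusion.** The concern holds in conditional form. The two SAPs share a model and a fallback, and only the placebo-controlled SAP protects the standard errors when the fallback is used. If a structured covariance is adopted for the OLE analysis and does not fit, the early- versus late-start standard errors and p-values may be invalid.

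Under assumed random slopes, nominal 5% tests at Weeks 52 to 76 have roughly 6 to 10% error, reaching 11.2% in the most extreme setting, while tests at the earliest visits are conservative. Under correlation decaying with calendar time the range is 4.9 to 6.4%.

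These figures are large-sample values that rest on assumed covariances and dropout, not on trial data. The textual difference between the SAPs is certain; the size of its effect is not. It is worth correcting because it is cheap and otherwise leaves the choice of variance open until after the data are seen.

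**What to change.** In OLE SAP 5.4, add the rule already in placebo-controlled SAP 5.1.4: when a structured covariance replaces the unstructured one, take the variance of the treatment effect from the sandwich estimator.

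For that case, name a degrees-of-freedom method compatible with the sandwich, such as between-within, in place of Kenward-Roger, which adjusts the model-based variance. Placebo-controlled SAP 5.1.4 names both without saying how they combine, so the same clarification would help there.

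Because an uncorrected sandwich can be anti-conservative with few subjects, either apply it with the sparse visits that 5.4 already allows to be excluded left out, or use a small-sample-corrected sandwich. A degrees-of-freedom change alone would not cure that problem.

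The cost is one or two sentences and a program option, with slightly noisier standard errors when the structure happens to be right.

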6 SAFETY DATA

6.1 General Considerations

6.1.1 Analysis population

Safety population will be used for safety analyses of AEs, clinical laboratory data, [REDACTED] data, ECG data, and vital signs data. The safety MRI population will be used for the analysis of safety MRI data.

6.1.2 Analysis period and analysis displays

The analysis period will be specified for each output. Analysis periods in this SAP are:

- OLE period – for AE analyses
- active treatment (placebo-controlled and OLE) period - for all safety analyses

Safety data will be summarized by OLE treatment group (BIIB092 early start, BIIB092 late start, and in addition BIIB092 total).

6.1.3 Visit windows

Visit windows will be mutually exclusive, contain no gaps, and end at the midpoint between scheduled post-baseline visits, with the midpoint itself assigned to the subsequent visit window. If two or more evaluations occur in the same visit window, the evaluation closest to the target visit day will be selected for inclusion in the analysis. If multiple evaluations on different days are equally close to the target visit day, then the latest evaluation will be selected for inclusion in the analysis. If multiple evaluations occur on the same day, the earliest value will be chosen for analysis if time of collection is available; a scheduled value will be chosen before an unscheduled or early discontinuation record.

6.1.4 Incidence, incidence proportion and incidence rate

- Incidence and incidence proportion will be provided in incidence proportion tables. Incidence is defined as the number of subjects who experienced an event. Incidence proportion is defined as the number of subjects who experienced an event divided by total number of subjects in the analysis population, i.e., percentage. Each subject will be counted only once within each category.

- Incidence and incidence rate will be provided in incidence rate tables. Two different kinds of incidence rate tables will be provided as appropriate for different analyses. Definitions are provided below.
 - Follow-up adjusted incidence rate (FAIR) – defined as the number of subjects with an event divided by the total follow-up time among the subjects in the analysis population (e.g., incidence rate per 100 subject-years). The total follow-up time (subject-years) is the sum of all subjects' follow-up time, where a subject's follow-up time is calculated as the number of days (inclusive) from first dose of treatment until the last day on study divided by 365.25. For active treatment period analyses, the first dose of treatment is considered the first dose received in the study period (PC or OLE) in which a subject first receives BIIB092. Each subject will be counted only once within each category.
 - Exposure-adjusted incidence rate (EAIR) – defined as the number of subjects with an event divided by the total exposure adjusted follow-up time (i.e. total time at risk for the event) among the subjects in the analysis population (e.g., incidence rate per 100 subject-years). The exposure adjusted follow-up time (time at risk for the event) for a subject is the time from the first dose of study drug in the first BIIB092 dosing period (PC or OLE) to the initial occurrence of the event for subjects who experienced the event, and is the time from first dose of study drug in the first BIIB092 dosing period to the end of follow-up (the last day on study) for subjects who did not experience the event. The total time at risk is the sum of all subjects' time at risk. Each subject will be counted only once within each category.

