3.2 Analysis Period

Depending on the purpose, different analyses will be conducted on the following study periods:

1. **OLE period**. Only data in the OLE period will be included in these analyses. This OLE analysis period will be applied to all the AE analyses, and the analyses will include all subjects who were dosed in the OLE period.
2. **Placebo-controlled and OLE period**. All the data in the placebo-controlled and OLE periods will be included in these analyses. This analysis period will be applied to all efficacy analyses. The analyses will include all subjects who were dosed in the study including those who did not enroll into the OLE period.
3. **Active treatment (placebo-controlled and OLE) period**. The active treatment period is defined as the study period(s) in which a subject received BIIB092. For early start subjects, all data from placebo-controlled and OLE periods will be included. For late start subjects,

only data in the OLE period will be included. This analysis period will be applied to all safety analyses, and the analyses will include all subjects who were dosed in the study except for subjects who received only placebo in the placebo-controlled period and did not get dosed in the OLE period.

For a given output, both the analysis population and the analysis period will determine which subjects will be included. For example, the incidence table of adverse events in the OLE period will include subjects in the safety population for the OLE period, i.e., all randomized subjects who received at least one dose of study treatment in the OLE period. The incidence rate table of adverse events in the active treatment (placebo-controlled and OLE) period will include subjects in the safety population for the active treatment period, i.e., all randomized subjects who received at least one dose of treatment in the active treatment period. In this SAP we do not separately define the analysis population in each analysis period.

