6.2.2 Summary and incidence analysis

Overall summary of AE table will be done for the OLE period, as well as for the active treatment (placebo-controlled and OLE) period presented by OLE treatment group. The following information will be summarized: the number of subjects with any AE, with any AE by maximum severity (as assessed by the investigator), the number of subjects with any related AE (related to study drug as assessed by investigator), the number of subjects with SAE, the number of subjects with related SAE, the number of subjects with AE leading to study drug discontinuation, the number of subjects with an AE that led to withdrawal from the study and the number of subjects with a fatal event.

The sorting order for AE incidence tables, unless otherwise specified, will be by decreasing frequency order of “BIIB092 total” column within each category in the tables presented by OLE treatment group. A subject is counted only once within each category in each table. For example, for the table of AEs by system organ class and preferred terms sorted by decreasing frequency presented by treatment group, system organ class will be presented in decreasing frequency order of BIIB092 total column, and within each system organ class, preferred terms will be presented in decreasing frequency order of BIIB092 total column. A subject is counted only once within each system organ class and preferred term.

The following AE incidence proportion tables will be provided for the OLE period (presented by the OLE treatment group unless otherwise specified):

1. AEs by system organ class and preferred term sorted by decreasing frequency
2. AEs by system organ class and preferred term sorted by alphabetical order
3. AEs by system organ class, high level group term and preferred term
4. AEs by system organ class
5. AEs by preferred term
6. AEs with an incidence of 2% or more in any treatment group by preferred term
7. AEs with an incidence of 5% or more in any treatment group by preferred term
8. Severe or very severe AEs by system organ class and preferred term
9. Severe or very severe AEs by preferred term

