10. AEs by maximum severity by system organ class and preferred term. (System organ class will be presented alphabetically. Preferred terms will be presented in decreasing frequency order. Maximum severity will be presented within each preferred term in the order of mild, moderate, severe, very severe, unknown and total. A subject will be counted only once at the maximum severity within each system organ class and preferred term.)
11. AEs by maximum severity by preferred term. (Preferred terms will be presented in decreasing frequency order. Maximum severity will be presented within each preferred term in the order of mild, moderate, severe, very severe, unknown and total. A subject will be counted only once at the maximum severity within each preferred term.)
12. Related AEs by system organ class and preferred term
13. SAEs by system organ class and preferred term
14. SAEs by preferred term

15. Related SAEs by system organ class and preferred term
16. AEs that led to discontinuation of study treatment by system organ class and preferred term
17. AEs that led to withdrawal from study by system organ class and preferred term
18. SAEs with fatal outcome by system organ class and preferred term
19. AEs by 12-week intervals by system organ class and preferred term
20. SAEs by 12-week intervals by system organ class and preferred term

In addition to listings provided as part of the analysis described in the placebo-controlled SAP, a listing of AEs that led to withdrawal from study will be provided.

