6.2.5 Infusion reactions

Infusion reactions will be identified through 1) temporal association, defined as those events which occur on the day of an infusion or the subsequent two calendar days after an infusion; and 2) through a custom MedDRA search of preferred terms. The list of custom MedDRA search terms can be found in Appendix 11.2. A serious infusion reaction is a serious adverse event which is identified by one or both methods.

For the OLE period, an overall summary of infusion reactions will be provided with the number of subjects (n, %) with any infusion reaction; with any infusion reaction identified by temporal association only; with any infusion reaction identified through the custom search only; and any infusion reaction identified through both methods. Additionally, the following incidence proportion tables will be provided for the OLE period:

1. Infusion reactions (temporal association or custom search) by SOC and PT
2. Serious infusion reactions (temporal association or custom search) by SOC and PT
3. Infusion reactions (temporal association or custom search) for subjects with and without positive treatment emergent ADAs by PT
4. Serious infusion reactions (temporal association or custom search) for subjects with and without positive treatment emergent ADAs by PT
5. Infusion reactions that occurred in temporal association to an infusion by physical location of infusion (in-clinic vs. home) by SOC and PT
6. Serious infusion reactions that occurred in temporal association to an infusion by physical location of infusion (in-clinic vs. home) by SOC and PT
7. Infusion reactions identified through custom search criteria by PT
8. Infusion reactions (temporal association or custom search) by 12-week intervals by PT

Positive treatment emergent ADA will be based on the definition in Section 8 using the integrated placebo-controlled and open label extension data.

An exposure adjusted incident rate table for infusion reactions will be provided for the active treatment (placebo-controlled and OLE) period.

Additionally, the following incidence proportion tables will be provided for the active treatment (placebo-controlled and OLE) period:

1. Infusion reactions that occurred in temporal association to an infusion by physical location of infusion (in-clinic vs. home) by SOC and PT
2. Serious infusion reactions that occurred in temporal association to an infusion by physical location of infusion (in-clinic vs. home) by SOC and PT

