20. SAEs with fatal outcome by SOC and PT
21. AEs by 12-week intervals by SOC and PT
22. SAEs by 12-week intervals by SOC and PT

The following listings will be provided.

1. Listing of AEs
2. Listing of SAEs (including pre-dosing SAEs)
3. Listing of AEs that led to discontinuation of study treatment
4. Listing of SAEs with fatal outcome

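### OLE SAP tables by 12-week interval divide by everyone dosed in the OLE, so under staggered follow-up a constant risk is displayed as falling and a rising risk is masked

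*SAP*

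**What the plan says.** OLE SAP 6.1.4 gives a single definition for every incidence proportion table: "Incidence proportion is defined as the number of subjects who experienced an event divided by total number of subjects in the analysis population".

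OLE SAP 6.2.2 opens its numbered list with "The following AE incidence proportion tables will be provided for the OLE period". Item 19 is "AEs by 12-week intervals by system organ class and preferred term" and item 20 is "SAEs by 12-week intervals by system organ class and preferred term". Section 6.2.5 has a further list of incidence proportion tables for the OLE period, whose item 8 is "Infusion reactions (temporal association or custom search) by 12-week intervals by PT".

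OLE SAP 3.2 (Analysis Period) uses the OLE-period AE incidence table as its example and takes the population to be "all randomized subjects who received at least one dose of study treatment in the OLE period". Length of follow-up plays no part. No section gives a separate denominator for tables split by interval.

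On timing, OLE SAP 3.1 places the interim analysis at the point where all subjects have completed the placebo-controlled period, and 1.1 says OLE duration depends on enrolment date. Section 5.3 drops two analyses with the words "Because too few patients will have reached Week 100 at the time of interim analysis database lock". Week 100 is OLE week 48 (100 − 52).

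The placebo-controlled SAP repeats the definition in 6.1.3 and also has interval tables: 6.2.2 items 7, 8, 21 and 22 (item 22 is "SAEs by 12-week intervals by SOC and PT") and 6.2.4 item 5.

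**The concern.** A table split by time since OLE start will be read across its columns as a picture of how risk changes. That reading works only if each column is divided by the subjects, or the time, actually observed in that interval. Under 6.1.4 every column has the same denominator. Subjects who have withdrawn, or who entered the OLE too recently to have reached the interval, add to the denominator and cannot add to the numerator. The displayed percentage then tracks shrinking follow-up as well as risk, and the error runs in the reassuring direction. The protocol synopsis makes long-term safety and tolerability the primary objective of the extension.

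No other planned output corrects this. The follow-up-adjusted rates (6.2.3) and exposure-adjusted rates (6.2.4, 6.2.5) cover the whole active treatment period and are not split by interval.

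**Working it through.** The plan states no figure for these tables, so there is none to reproduce. The size has to be illustrated under assumptions.

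**Inputs.** From the documents: the denominator, the OLE population, the staggered entry and the scarcity of subjects at OLE week 48 quoted above; dropout of about 25% through Week 52 (protocol 17.1). Assumed: OLE follow-up at the cut uniform over 0 to T weeks; a constant hazard of h = 0.5 per subject-year; each subject counted at most once per interval, with each interval counted afresh.

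**Formula.** Put x = 12h/52 = 0.1154. A subject observed for a full interval has risk 1 − exp(−x) = 10.9%. A subject whose follow-up ends at a uniformly distributed point within the interval has average risk 1 − (1 − exp(−x))/x = 5.6%. The displayed percentage is

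(fraction fully observed) × 10.9% + (fraction partly observed) × 5.6%,

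with both fractions taken over all OLE-dosed subjects.

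**T = 48 weeks**

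| OLE weeks | Fully observed | Partly observed | True risk | Shown under 6.1.4 | Divided by those entering the interval |
|---|---|---|---|---|---|
| 0–12 | 0.75 | 0.25 | 10.9% | 9.6% | 9.6 / 1.00 = 9.6% |
| 12–24 | 0.50 | 0.25 | 10.9% | 6.8% | 6.8 / 0.75 = 9.1% |
| 24–36 | 0.25 | 0.25 | 10.9% | 4.1% | 4.1 / 0.50 = 8.2% |
| 36–48 | 0 | 0.25 | 10.9% | 1.4% | 1.4 / 0.25 = 5.6% |

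The last column shows that changing the denominator alone leaves a residual decline, because some subjects entering an interval are seen for only part of it.

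**Rate within the interval.** Mean follow-up per OLE subject in the four intervals is 12 × (fully observed) + 6 × (partly observed) = 10.5, 7.5, 4.5 and 1.5 weeks. Dividing the shown proportion by that time in years (for example 0.0956 / (10.5/52)) gives between 47 and 48 per 100 subject-years in every interval, which is essentially flat. If time is stopped at the first event in the interval, the rate is 50 throughout.

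**Rising risk, T = 48.** Let the hazard be 0.5, 0.625, 0.75 and 0.875 in successive intervals. The same formula gives true risks of 10.9, 13.4, 15.9 and 18.3%, displayed as 9.6, 8.4, 6.0 and 2.4%.

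**Sensitivity to follow-up.** With T = 60 the constant-risk series is 9.8, 7.6, 5.5, 3.3 and 1.1%. A separate calculation used a constant 20% risk per 12 weeks and exponential dropout of 25% per 52 weeks:

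- uniform 0–48 weeks: 17.1, 11.4, 6.5, 2.1% (with 10% risk, 8.5% falling to 1.0%)
- uniform 12–60 weeks: 19.4% falling to 6.0% by weeks 36–48
- uniform 0–96 weeks: 18.2% falling to 9.0% by weeks 36–48
- dropout only, no staggering: 19.4% falling to 15.9% by weeks 36–48

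The decline appears in every case; its steepness depends on the follow-up assumed.

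**Placebo-controlled period.** Follow-up is fixed at 52 weeks, so only dropout acts. With linear 25% dropout the mean fraction in follow-up is 1 − 0.25t/52 at t = 6, 18, 30 and 42 weeks: 0.971, 0.913, 0.856 and 0.798. A flat risk appears to fall by 1 − 0.798/0.971 = 18% in relative terms.

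**The case against.** The definition in 6.1.4 is general and is not restated beside the interval tables. The table shells are not in the documents, and a programmer might use the number at risk. That is possible, but the written rule says otherwise, and a plan should not depend on an unwritten departure from it.

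These are descriptive tables, tied to no test or decision rule, and only three of the 28 OLE incidence proportion tables listed in 6.2.2 and 6.2.5. The adjusted rates give a sound overall picture, OLE SAP 4.1 and 4.3 report disposition and weeks on treatment, and placebo-controlled SAP 4.1 tabulates withdrawal on nearly the same 12-week grid. All of this limits the harm. None of it lets a reader recover OLE interval-specific risk.

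Four stronger readings are tempting and should not be drawn:

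- A reader might infer that risk will appear to fall with time on BIIB092. The intervals run on OLE time, which equals time on drug only for late-start subjects; early-start subjects enter after up to 52 weeks of treatment.
- A reader might infer that both SAPs prescribe the same wrong denominator throughout. Placebo-controlled SAP 6.2.2 calls its list incidence tables, and 6.1.3 defines incidence as a count of subjects. Only 6.2.4 item 5 is expressly an incidence proportion table. For the AE and SAE interval tables the denominator is unspecified.
- A reader might infer a spurious difference between arms in the placebo-controlled period. That needs differential dropout, for which the documents give no figure. An assumed 20% versus 30% leaves 0.838 versus 0.758 in the last interval, a ratio of 1.11. At 10.9% risk that is about 9.1% versus 8.3%, under one percentage point.
- A reader might take the longer follow-up scenarios as forecasts. Uniform 0–60 weeks puts 12/60 = 20% of subjects past OLE week 48, which fits poorly with the SAP's own statement that too few will have got there.

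**Conclusion.** The point holds for the three OLE interval tables: AEs, SAEs and infusion reactions. Applied as written, 6.1.4 makes the displayed percentage decline over OLE time when the true risk is constant, and it understates or reverses a rise. The direction follows from the definition and the staggered follow-up. The size is not fixed by the documents: 9.6% to 1.4% over four intervals, against a true 10.9% in each, assumes uniform 0–48 week follow-up and a hazard of 0.5 per subject-year. If a subject were counted only in the interval of the first event, which the SAP does not settle, the fall would be steeper still.

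In the placebo-controlled period the effect is modest, about 18% relative under the assumed linear dropout. It applies to the infusion-reaction interval table, and to the AE and SAE interval tables only if percentages are shown.

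**What to change.** In OLE SAP 6.1.4, add that tables by 12-week interval will show, for each interval:

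- the number of subjects in follow-up at its start, as the denominator and in the column header;
- the number and percentage of those subjects with an event, each subject being counted once in each interval in which an event occurs;
- the rate per 100 subject-years of follow-up within the interval.

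State that intervals are to be compared on the rate, because the at-risk percentage still declines when intervals are partly observed. Refer to this rule from 6.2.2 items 19 and 20 and from 6.2.5 item 8.

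Add the same wording to placebo-controlled SAP 6.1.3, to govern 6.2.4 item 5 and, if percentages are shown, 6.2.2 items 7, 8, 21 and 22.

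The cost is a short paragraph in each SAP, a changed denominator and an added rate column in the table shells, and the programming of interval follow-up time. No new data are needed. The change should be made before the tables are produced.
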